### **8.1.1 Solicited Adverse Events**

Solicited AEs are predefined AEs that can occur after study product administration, may be expected to occur if the study product is insufficiently attenuated, and have protocol-specific criteria for reporting.

Solicited AEs, whether identified by a parent/guardian or clinician, are only recorded on CRFs if they meet the definitions per Appendix IV Individual symptoms listed in the “events” column that fail to meet the criteria in the “definition” column in Appendix IV are recorded in source documents but are not recorded on the CRFs. During the Acute Phase of this study, days 0 through 10 for RSV-seropositive participants and days 0 through 28 for RSV-seronegative participants, solicited AEs meeting the criteria for reporting will be recorded on CRFs, assigned a severity grade (Section 8.2), and assessed for relationship to study product (see Section 8.1).

Solicited AEs are defined in Appendix IV and include the following:

1. Fever
2. URI
  - a. Rhinorrhea,
  - b. Pharyngitis,
  - c. Cough without LRI, or
  - d. Hoarseness
3. Otitis Media
4. LRI
  - a. Wheezing,
  - b. Pneumonia,
  - c. Laryngotracheobronchitis (croup),
  - d. Rhonchi, or
  - e. Rales

#### *Solicited AEs Elicited by History Unconfirmed by Clinical Assessment*

With the exception of fever, solicited AEs reported by parents/guardians are NOT recorded on CRFs if a clinical assessment done on the day of the event(s) does/did not confirm their presence. For example, if a parent/guardian reports rhinorrhea on the day of visit, and there is/was no rhinorrhea upon exam, then the participant is considered to not have rhinorrhea that day.

If the parent/guardian report of a fever meets the “definition” column criteria in Appendix IV on a day on which there was a clinical assessment, the fever will be recorded on CRFs regardless of whether the clinical assessment confirmed its presence.

Events elicited by parent/guardian history for days on which there was no clinical exam will be:

- 1) Recorded on the CRFs as AEs if the parent/guardian description meets the “definition” column criteria in Appendix IV.
- 2) Recorded only on the source document, and NOT on the CRF, if the parent/guardian description fails to meet the “definition” column criteria in Appendix IV. For example, both rhinorrhea and cough must each occur on 2 consecutive days to meet the definition required for reporting per Appendix IV.

## 8.1.2 Serious Adverse Events

A SAE is an AE, whether considered related to the study product or not, that meets one or more of the following criteria:

1. Results in death during the period of protocol-defined surveillance.
2. Is life threatening: defined as an event in which the participant was at immediate risk of death at the time of the event; it does not refer to an event that hypothetically might have caused death were it more severe.
3. Requires inpatient hospitalization (or prolongation of existing hospitalization): defined as at least an overnight stay in the hospital or emergency ward for treatment that would have been inappropriate if administered in the outpatient setting.
4. Results in a persistent or significant disability/incapacity.
5. Is a congenital anomaly or birth defect.
6. Is an important medical event that may not be immediately life threatening or result in death or hospitalization but may jeopardize the patient or may require intervention to prevent one of the outcomes listed above.

## 8.1.3 Unexpected Adverse Event

An AE is unexpected if it is not listed in the Investigator's Brochure or Package Insert (for marketed products) or is not listed at the specificity or severity that has been observed. It is the responsibility of the IND Sponsor to make this determination.

## 8.2 GRADING THE SEVERITY OF ADVERSE EVENTS

The Investigator will assess all AEs with respect to **Seriousness** (criteria listed above), **Severity** (intensity or grade), and **Causality** (relationship to study agent and relationship to research). All AEs and fever will be graded using the protocol-defined grading system.

### 8.2.1 AE Grading

**Table 21: Grading for Adverse Events**

Severity	Defined
Grade 1 Mild	No medical intervention required; may include over-the-counter medications managed by the participant or caregiver for treatment of symptoms
Grade 2 Moderate	Outpatient medical intervention by a health care provider required; may include use of over-the-counter and/or prescription medications
Grade 3 Severe	Prolonged medical intervention and/or hospitalization required
Grade 4 Life threatening	Illness requiring hospitalization with intensive care
Grade 5 Death	Event resulting in fatal outcome to the participant

## 8.2.2 Fever Grading

**Table 22: Grading for Fever**

Severity	Defined
Grade 1	$\geq 100.4^{\circ}\text{F}$ but $\leq 101.4^{\circ}\text{F}$
Grade 2	$\geq 101.5^{\circ}\text{F}$ but $\leq 102.4^{\circ}\text{F}$
Grade 3	$\geq 102.5^{\circ}\text{F}$ but $\leq 104.8^{\circ}\text{F}$
Grade 4	$\geq 104.9^{\circ}\text{F}$

Applies to any modality of temperature measurement

## 8.3 PAUSING AND STOPPING RULES

If any of the following occur in a participant during the specified period after receiving the study product, additional enrollment/inoculations will be temporarily suspended at all sites (Table 23).

**Table 23: Pausing and Stopping Rules**

Specified Phase	Event	Reporting
Acute and Post-Acute Days 0 through 28 following inoculation for RSV-seropositive subjects and days 0 through 56 following inoculation for RSV-seronegative subjects	An SAE that cannot be attributed to an etiology or cannot be attributed to a cause unrelated to the study product.	A description of the vaccine-associated AE(s) or safety issue must be reported by the PI or study staff, within one business day of the PI's awareness, to the CSO and the DSMB by fax or email.
Acute Only Days 0 through 10 following inoculation for RSV-seropositive subjects and days 0 through 28 following inoculation for RSV-seronegative subjects	An LRI per Appendix IV , OR A fever of Grade 4 OR Any Grade 3 or above solicited AE (other than fever)	

The regulatory sponsor (OCRPRO) will determine if the FDA needs to be notified. The DSMB and regulatory sponsor will be informed and receive pertinent data of the event by the PI. Follow-up visits for participants already inoculated will continue as outlined in [Appendix II \(Table 30\)](#).

If the event is determined to have occurred in a participant who received active agent (vaccine), and the event meets one of the following stopping rule criteria, then the event will be reviewed by the DSMB prior to resuming enrollment.

1. One or more participants experience an SAE that cannot be attributed to an etiology or cannot be attributed to a cause unrelated to the study vaccine, OR
2. One or more participants develop LRI associated with shedding of vaccine virus at the time of the LRI (even if another pathogen is identified, unless the RSV is confirmed to be wt RSV), OR
3. One or more participants develop LRI that is not explained by a diagnosis unrelated to the vaccine virus, OR
4. One or more participants experiences a Grade 4 fever or any Grade 3 or Grade 4 solicited AE other than fever associated with shedding of vaccine virus, OR
5. Any pattern of research laboratory values or clinical symptoms is observed that the protocol team considers a significant safety issue for participants.

The DSMB will notify the PI (via the study sponsor) of their recommendations as to whether enrollment can resume, or if the study needs to be stopped. The regulatory sponsor (OCRPRO) will be informed about this decision. In the event of an SAE, the study may be resumed if it can be demonstrated to the DSMB that there is no proven causal relationship with the vaccine.

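### Section 8.3 lets the study resume after an SAE if causation is not proven, a test that the unexplained SAE causing the pause already passes

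*Combined protocol and SAP*

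**What the plan says.** Section 8.3 works in three steps.

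- **Pause.** If a Table 23 event occurs, "additional enrollment/inoculations will be temporarily suspended at all sites". One of the four triggers is an SAE, through Day 28 in seropositive and Day 56 in seronegative children, for which no etiology, or no unrelated cause, can be found. The PI or study staff report the event within one business day "to the CSO and the DSMB by fax or email".
- **Review.** If the child received vaccine and a stopping criterion is met, "then the event will be reviewed by the DSMB prior to resuming enrollment". Criterion 1 mirrors the SAE trigger. It applies when any child is found to "experience an SAE that cannot be attributed to an etiology or cannot be attributed to a cause unrelated to the study vaccine".
- **Release.** The Board recommends whether enrolment can resume or the study must stop. The section then adds, for SAEs: "the study may be resumed if it can be demonstrated to the DSMB that there is no proven causal relationship with the vaccine".

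Two other sections bear on this. Section 8.1 uses a two-way causality scale: an event is Related if there is a reasonable possibility of a link to the study drug, and Not related if there is none. Section 9.4.2 has the PI notify the Board when a pausing or halting criterion is met and obtain its recommendation on continuing, modifying or ending the study.

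**The concern.** The test for starting the pause and the test for ending it point in opposite directions. The pause starts because the vaccine cannot be ruled out. It may end because the vaccine has not been proved responsible. Ruling out and failing to prove are different standards, and an unexplained event lies between them.

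This matters because the product is a live virus in its first human study (Section 1.2.3), given in Group 2 to seronegative infants from 6 months of age (Section 4.3). A single unexplained SAE in a vaccinee is the situation in which the Board most needs a clear standard. The release sentence offers a standard weaker than the protocol's own definition of Not related, and one that screens out almost nothing.

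**Working it through.** No figure in the plan is in dispute. The check sets the SAE trigger, the Section 8.1 scale and the release sentence side by side for each state of knowledge about an SAE in a vaccinee.

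| What is known about the SAE | Triggers the pause and criterion 1? | Section 8.1 class | Meets the release test? |
|---|---|---|---|
| Attributed to an unrelated cause | No | Not related | Yes, but no SAE pause to release |
| No etiology found | Yes | Related, if a link is a reasonable possibility | Yes |
| Vaccine suspected, not proved | Yes | Related | Yes |
| Vaccine proved to be the cause | Yes | Related | No |

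1. **Second row.** If no etiology can be found, no causal link to the vaccine has been proved. The event that starts the pause therefore satisfies the release test on the same day, with no further information.
2. **Third row.** A reasonable possibility is enough for Related and is less than proof. An SAE that the investigator classes as Related can therefore pass the release test.
3. **Fourth row.** Of the three states that trigger the pause, only proved causation fails the release test. Proof of causation from a single event will seldom be available.
4. **The duty to demonstrate.** The sentence requires a demonstration to the Board, but what must be demonstrated is only that proof is absent. In rows two and three this is true from the start.

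**Reach.** The SAE trigger is one of four in Table 23. The others are LRI, Grade 4 fever, and any other solicited AE of Grade 3 or above. The release sentence speaks only of SAEs. The planned vaccinees in Table 1 number 10 + 14 = 24 to 10 + 20 = 30.

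**The case against.** The strongest reply is that the release sentence does not act alone. One event is enough to suspend enrolment at all sites. For a vaccinee's unattributed SAE, Board review before restart is mandatory under criterion 1. The sentence says only that the study may resume, it puts the burden of demonstration on the study, and the Board is free to recommend stopping. All of this stands. A reader might infer from the wording that an unexplained SAE releases its own pause. The documents do not support that, because a Board decision always lies between the event and the restart. What remains is that the one criterion written down for that decision is too weak and does not use the protocol's own causality term.

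A second reply is that any workable rule must let the Board restart after an unexplained event, so a tighter sentence changes little. This is partly right. The change proposed below keeps that discretion. It replaces an undefined, weak criterion with the Section 8.1 term and requires recorded reasons when the cause stays unknown.

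A wider reading is also tempting. The explicit review clause in Section 8.3 begins "If the event is determined to have occurred in a participant who received active agent (vaccine), and the event meets one of the following" stopping criteria, so a reader might infer that pauses in placebo recipients, or pauses in vaccinees that meet no criterion, can be lifted without the Board. The documents do not support this either. Section 8.3 says of every pause: "The DSMB and regulatory sponsor will be informed and receive pertinent data of the event by the PI". Section 9.4.2 requires a Board recommendation on continuation for any pausing criterion, with no limit by arm, shedding or diagnosis. It does not literally say that the recommendation must precede the restart, but during a suspension that is its natural meaning. Section 8.3 simply lacks a cross-reference.

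**Conclusion.** The point holds for the release sentence and should be fixed. As written, the test for resuming after an SAE is already met by an unexplained SAE when it triggers the pause, and it can be met by one classed as Related. The fault lies in the standard handed to the Board, not in whether the Board is involved.

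Its extent is one sentence governing one of four pause triggers. The documents give no expected rate of unattributed SAEs, so neither the number of affected pauses nor the chance of one can be stated. The conclusion rests on the ordinary meaning of proven and on the Section 8.1 definitions. It does not assume that the Board would use the weak standard; a careful Board would probably apply a stricter one on its own initiative. The relation of Section 8.3 to Section 9.4.2, and the wording of criterion 4, are matters of clarity and not errors.

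**What to change.** Replace the last sentence of Section 8.3 with:

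> In the event of an SAE in a vaccine recipient, enrollment may resume only if the DSMB, after review, concludes that there is no reasonable possibility that the SAE was related to the vaccine (Section 8.1), or, if the cause remains undetermined, documents why the risk to further participants is acceptable and any added safeguards.

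Two optional clarifications could go into the same amendment:

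- Cross-refer Section 8.3 to Section 9.4.2, so that the need for a Board recommendation after every pause is visible where staff will look for it.
- State in criterion 4, which covers a participant who "experiences a Grade 4 fever or any Grade 3 or Grade 4 solicited AE other than fever associated with shedding of vaccine virus", whether the shedding condition also applies to Grade 4 fever. On either reading such a fever pauses enrolment and is reported to the Board.

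The cost is a short amendment. A pause after an unexplained SAE may last somewhat longer, which uses part of the April 1 to October 31 enrolment window (30 + 31 + 30 + 31 + 31 + 30 + 31 = 214 days). Seronegative children whose 42-day screening window lapses meanwhile would need rescreening under Section 6.4.1. Sample size and analyses are unaffected.

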## **9 STATISTICAL CONSIDERATIONS**

### **9.1 GENERAL DESIGN ISSUES**

#### **9.1.1 General Design**

The goal of this phase I, blinded, randomized, placebo-controlled vaccine trial is to assess the safety, infectivity, and immunogenicity of the RSV 6120/ΔNS2/1030s vaccine candidate in RSV-seropositive and RSV-seronegative pediatric participants. Fifteen RSV-seropositive participants will be randomized in a 2:1 ratio to receive either the candidate vaccine at a dose of  $10^{5.7}$  PFU or placebo. Twenty-one to thirty RSV-seronegative participants will be randomized in a 2:1 ratio to receive either the candidate vaccine at a dose of  $10^{5.0}$  PFU or placebo.

#### **9.1.2 Description of the Statistical Methods to be Employed**

This study, like other phase I studies, is exploratory, rather than confirmatory; its purpose is to assess frequencies of AEs and patterns of immune responses. Descriptive approaches will be used to meet the protocol objectives as stated in Section 2 of this protocol, as well as formal statistical tests as outlined in Section 9.5.

## **9.2 OUTCOME MEASURES**

### **9.2.1 Primary Outcome Measures**

*Safety: Types and grades of study product-related:*

- Solicited AEs as defined in Appendix IV from Study Days 0-10 for RSV-seropositive and Study Days 0-28 for RSV-seronegative participants
- Unsolicited AEs from Study Days 0-10 for RSV-seropositive and Study Days 0-28 for RSV-seronegative participants
- SAE (Section 8.1.2) from Study Days 0-28 for RSV-seropositive and Study Days 0-56 for RSV-seronegative participants

*Infectivity:*

- Infection with RSV as defined as
  - 1) vaccine virus identified in a nasal wash from Study Days 0-10 for RSV-seropositive and Study Days 0-28 for RSV-seronegative (a binary outcome based on nasal washes done throughout the study period; Day 0 nasal wash will be counted as baseline); or
  - 2)  $\geq 4$ -fold rise in RSV neutralizing antibody titer from Study Days 0-28 for RSV-seropositive and Study Days 0-56 for RSV-seronegative subjects
- Peak titer of vaccine virus shed from Study Days 0-10 for RSV-seropositive and Study Days 0-28 for RSV-seronegative subjects
- Duration of virus shedding in nasal washes as determined by a) culture and b) RT-PCR from Study Days 0-10 for RSV-seropositive and Study Days 0-28 for RSV-seronegative subjects

*Immunogenicity:*

- $\geq 4$ -fold rise in RSV-neutralizing antibody titer from study entry to Study Day 28 for RSV-seropositive and from study entry to Study Day 56 for RSV-seronegative subjects
- $\geq 4$ -fold rise in IgG antibody responses to RSV F glycoprotein (ELISA) from study entry to Study Day 28 for RSV-seropositive and from study entry and Study Day 56 for RSV-seronegative subjects

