# **2 OBJECTIVES**

## **2.1 PRIMARY OBJECTIVES**

### *Safety*

1. To assess the frequency and severity of study product-related solicited and unsolicited AEs in RSV-seropositive participants (group 1) from day 0 through the 10th day following inoculation
2. To assess the frequency and severity of study product-related solicited and unsolicited AEs in RSV-seronegative participants (group 2) from day 0 through the 28th day following inoculation
3. To assess study product-related serious adverse events (SAEs) in RSV-seropositive participants (group 1) from day 0 through the 28th day following inoculation
4. To assess study product-related SAEs in RSV-seronegative participants (group 2) from day 0 through the 56th day following inoculation

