## 4 STUDY POPULATION

Approximately 15 RSV-seropositive children  $\geq$  12 months to  $<$  60 months of age will be enrolled; 10 will receive a single dose of  $10^{5.7}$  PFU of vaccine and 5 will receive a single dose of placebo. Subsequently, 21 to 30 RSV-seronegative infants and children  $\geq$  6 months to  $<$  25 months of age will be enrolled in the study and will receive a single dose of either  $10^{5.0}$  PFU of vaccine or placebo in a 2:1 ratio. These numbers were chosen based upon experience with phase I evaluation of other live-attenuated respiratory virus candidate vaccines ([11,23,25](#)) and statistical considerations (Section 9).

Placebo recipients are needed in pediatric studies to distinguish the background respiratory and febrile illnesses that occur in infants and children from those attributable to study vaccine. These numbers were chosen based upon experience with phase I evaluation of other live-attenuated respiratory virus candidate vaccines ([11,23,25](#)) and statistical considerations (Section 9).

Infants and children will be selected for participation according to the described study-specific co-enrollment considerations; the recruitment, screening, and enrollment process; and participant retention and withdrawal or termination.

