## **9.5 ANALYSES**

### **9.5.1 Assessment of Primary Objectives**

Safety data from all participants in CIR 322 who have been inoculated will be summarized together, including data from participants who discontinue study early or have some missed visits. In the immunogenicity analyses, those who do not provide data for the Day 28 Visit follow-up for RSV-seropositive participants and for the Day 56 Visit follow-up for RSV-seronegative participants (due to early discontinuation or missed visit) will be treated as “failures.” Sensitivity analyses will be performed to check if the results are consistent with those when these participants are excluded. Participants who receive any of the disallowed treatments listed in Section 5.10 during the first 28 days after inoculation for RSV-seropositive participants and during the first 56 days after inoculation for RSV-seronegative participants may be excluded from the immunogenicity evaluations after the time of the treatment. These participants, however, will be included in the safety evaluations for the duration of the study. These participants will not be replaced. Details of the analyses listed below will be included in the statistical analysis plan.

The frequency of solicited AEs and unsolicited AEs, along with 90% confidence intervals, during Study Days 0 to 10 in RSV-seropositive subjects and during Study Days 0 to 28 in RSV-seronegative subjects and of vaccine-related SAE during Study Days 0 to 28 in RSV-seropositive subjects and during Study Days 0 to 56 in RSV-seronegative subjects will be summarized. In addition, line listing of individual clinical solicited AEs and unsolicited AEs, graded by severity, will be prepared for events occurring during Study Days 0 to 10 in RSV-seropositive subjects and during Study Days 0 to 28 in RSV-seronegative subjects and vaccine-related SAE during Study Days 0 to 28 in RSV-seropositive subjects and during Study Days 0 to 56 in RSV-seronegative subjects.

The proportion of participants with infection defined as recovery of vaccine virus from a nasal wash as determined by culture and RT-PCR, and/or a  $\geq 4$ -fold rise in neutralizing antibody titer to RSV, will be summarized. A line listing of the individual peak titer of vaccine virus shed and duration of virus shedding in nasal washes by each individual will be prepared. In addition, the geometric mean peak titer and mean duration of virus shed will be provided for each treatment group.

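### The primary safety outcomes count only product-related events, the planned analysis filters only SAEs, and an SAE called unrelated after the acute phase appears in no planned summary or listing

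*Combined protocol and SAP*

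**What the plan says.** Section 9.2.1 introduces the three primary safety outcomes (solicited AEs, unsolicited AEs, SAEs) with "Types and grades of study product-related". The four safety objectives in 2.1 have the same limit; for the seronegative group, for example, "To assess study product-related SAEs in RSV-seronegative participants (group 2"). The AE windows are Days 0-10 (group 1) and 0-28 (group 2). The SAE windows are Days 0-28 and 0-56.

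Section 8.1 makes relatedness a two-way call by the study clinician, based on whether there is a reasonable possibility of a link, and allows the call to be revised as information arrives.

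Section 9.5.1 plans frequencies with 90% intervals and line listings for solicited and unsolicited AEs, and does not mention relatedness for them. For serious events, the same sentence promises the frequency "of vaccine-related SAE during Study Days 0 to 28 in RSV-seropositive subjects", with the matching Day 0-56 window for group 2. The line listing of SAEs has the same restriction.

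Section 4 gives the reason for the control arm: "Placebo recipients are needed in pediatric studies to distinguish the background respiratory and febrile illnesses" from illness caused by the vaccine. Section 6.3 withholds the code from clinical staff until every child in the randomization block has completed the acute phase.

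**The concern.** There are two problems.

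First, the outcome and its analysis differ. An analyst following 2.1 and 9.2.1 would drop every AE called unrelated. An analyst following 9.5.1 would keep all AEs and drop only unrelated SAEs. The two can give different headline safety results from the same data, and nothing says which governs.

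Second, a relatedness filter does by individual judgement what Section 4 assigns to the placebo arm. The solicited events are common childhood illnesses, and illness washes are tested for other viruses, so the judgement is hard. An all-cause comparison by arm does not depend on it. The filter matters most for SAEs after the acute phase, where the call may be made, or revised, by someone who knows the allocation. Once a child is known to have received placebo, the term vaccine-related in 9.5.1 has no clear meaning for that child, so the SAE table cannot serve as a fair comparison of the arms.

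**Working it through.** **1. Outcome against analysis.**

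| Event type | Outcome (2.1, 9.2.1) | Planned summary and listing (9.5.1) |
|---|---|---|
| Solicited AEs | product-related only | all |
| Unsolicited AEs | product-related only | all |
| SAEs | product-related only | vaccine-related only |

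The first two rows conflict. In the third row both columns are filtered, but with different terms: study product covers vaccine and placebo (Protocol Summary), while vaccine does not.

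**2. Which unrelated SAEs disappear.** Section 8.1.2 defines an SAE as an AE that meets a seriousness criterion. Section 8.1 divides AEs into solicited and all others, so every SAE is also a solicited or unsolicited AE. Under 9.5.1:

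- *Onset in the acute phase* (Days 0-10, group 1; Days 0-28, group 2): the event stays in the unfiltered AE summary and listing, whatever its relatedness call.
- *Onset on Days 11-28 (group 1) or 29-56 (group 2)*: the AE window has closed, so only the SAE table and listing could show the event. If called unrelated, it appears in neither.

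**3. Masking over those days.** The acute phase ends at Day 10 or Day 28 (6.5). Under 6.3 the code may be released once the last child in the block of three reaches that point. The SAE window then runs on for up to 18 days (28 − 10) in group 1 and 28 days (56 − 28) in group 2. The days on which an unrelated SAE can vanish are therefore the days on which its relatedness call may be unmasked. A later enrollee in the block can delay release, so unmasking is possible rather than certain.

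**4. Reproducing the plan's intervals.** The exact 90% upper limit for 0/n is 1 − 0.05^(1/n).

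- n = 20: 1 − 0.05^(1/20) = 0.139. Table 25 gives 14%.
- n = 10: 1 − 0.05^(1/10) = 0.259. Table 25 gives 26%.

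For 1/20 the lower limit is 1 − 0.95^(1/20) = 0.0026. The upper limit solves (1 − p)^20 + 20p(1 − p)^19 = 0.05, giving p = 0.216. This mirrors the plan's own 78% to 99.7% interval for 19/20 in 9.3.1.

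**5. Effect of omitting one SAE in a vaccinee.**

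| Vaccinees | SAE counted | SAE omitted |
|---|---|---|
| 20 (group 2 maximum) | 5% (0.3% to 22%) | 0% (0% to 14%) |
| 14 (group 2 minimum) | 7.1% (0.4% to 30%) | 0% (0% to 19%) |
| 10 (group 1) | 10% (1% to 39%) | 0% (0% to 26%) |

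The n = 14 row uses the same formulas. The n = 10 row is in Table 25. Table 25 is labelled for LRI or AEs; the interval depends only on the count and n, so it applies equally to SAEs.

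**6. If 9.2.1 rather than 9.5.1 governs AEs.** Table 24 has no relatedness filter. It reproduces for 20 vaccinees at a true rate of 10%: the chance of two or more events is 0.608 (stated 0.61). It describes the 9.2.1 outcome only if every true event is called related. Suppose a share q is so called; the documents give no value, so q is an assumption. Replacing 0.10 by 0.10q gives 0.55 at q = 0.9, 0.41 at q = 0.7 and 0.26 at q = 0.5. This shows what the 9.2.1 wording could cost. It is not an estimate for this trial and does not apply to the AE tables in 9.5.1.

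**The case against.** The strongest reply is that little is lost in practice. The planned AE tables are already all-cause. LRI, the sentinel event in 9.3.1, is a solicited AE, so an acute-phase LRI called unrelated stays in the summary and listing. Acute-phase calls are masked, and laboratory staff are kept apart from clinical assessment (6.10.2). A masked filter applied alike to both arms costs sensitivity but does not by itself favour one arm. Unrelated SAEs reach oversight: they are recorded on CRFs in both SAE windows (Tables 19 and 20) and reported to the sponsor and the DSMB (7.3). The trial is exploratory, with no formal safety comparison, and 9.5.1 leaves details to the statistical analysis plan.

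All of this stands, and it confines the point to outcome definition and reporting. It does not settle which text governs, or supply a summary or listing for unrelated post-acute SAEs.

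A reader might go further in three ways that the documents do not support:

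- *That every SAE called unrelated vanishes.* Acute-phase ones do not (step 2).
- *That AE rates will fall sharply because co-detected viruses prompt unrelated calls.* The documents give no co-detection rate and no share of such calls, and the 9.5.1 AE tables are unfiltered.
- *That the stopping rules reject causal judgement.* The shedding criterion for LRI in 8.3 does hold "even if another pathogen is identified, unless the RSV is confirmed to be wt RSV", but criteria 1 and 3 in the same list rest on attribution to an unrelated cause.

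**Conclusion.** The point holds as an inconsistency between outcome and analysis, with a specific reporting gap. Sections 2.1 and 9.2.1 filter all three safety outcomes on relatedness; 9.5.1 filters only SAEs. The gap covers SAEs called unrelated with onset on Days 11-28 in group 1 or Days 29-56 in group 2, a period when the call may be unmasked. With 20 vaccinees, one omitted event changes the reported SAE rate from 5% (about 0.3% to 22%) to 0% (0% to 14%).

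This rests on two assumptions: that 9.5.1 is applied as written, and that an acute-phase SAE is tabulated among the solicited and unsolicited AEs, as the definitions in 8.1 and 8.1.2 imply. If SAEs were removed from the AE tables, the gap would be wider. No sample-size figure or formal test in the plan is affected. It should be corrected before the analysis is fixed, because the correction is cheap and the present text allows two different primary safety results.

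**What to change.** In 2.1, 9.2.1 and 9.5.1, define the primary safety outcomes as all solicited AEs, all unsolicited AEs and all SAEs in the windows already stated, regardless of relationship to study product. State that they will be summarised and listed by treatment arm within each group; 9.5.1 promises this for titers and shedding but not for safety. Show the relatedness call and the adventitious-agent result as descriptive columns, and use one term (study product-related) throughout.

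The cost is a wording change and one added table column. Reported rates will be somewhat higher in both arms, and the text should say that they include background illness. No new data, visits or participants are needed, since Tables 19 and 20 already put these events on the CRFs.
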